20.4 SITE POOLABILITY ANALYSIS

A mixed effect model will be used to evaluate site heterogeneity by investigation of site effect and site by group interaction effect for the primary and secondary endpoints. [REDACTED]

[REDACTED]

[REDACTED]

[REDACTED]

[REDACTED]

20.5 VISUAL ACUITY CONVENTIONS AND GENERAL STATISTICS

Visual acuity data will be converted to LogMAR values prior to analysis and adjusted for the test distance used if it is not the standard distance for the chart. Descriptive statistics will typically include sample size (N), mean, standard deviation (SD), median, minimum (Min) and maximum (Max) as appropriate for continuous variables. For continuous variables, 2-sample t-test assuming normality will be used. For categorical data, the frequency and proportion will be reported, and Fisher's exact test or Chi-square test will be applied. For ordinal categorical data, the frequency and proportion will be reported with the Wilcoxon Rank-Sum test will be used.

20.6 INTERIM REPORTS

No interim study progress reports will be conducted for this study.

20.7 SAMPLE SIZE CALCULATION

Study sample sizes are based on the minimum of 100 evaluable subjects per study group for visual acuity. [REDACTED]

[REDACTED]

1. Monocular Best-corrected Distance Visual Acuity (BCDVA) at 4 m

For monocular best-corrected near visual acuity at 4 m (BCDVA), with 100 subjects in each lens group there is over 90% power to conclude non-inferiority in visual acuity between the test and control lens group at two-sided alpha of 0.10 with a non-inferiority margin of 1 line, assuming there is no difference between the IOLs and a standard deviation of 1.2 lines.

2. Monocular Distance-corrected Intermediate Visual Acuity at 66 cm (DCVA66)

For monocular distance-corrected intermediate visual acuity at 66 cm, with 100 subjects in each lens group, there is over 90% power at one-sided 0.025 alpha to detect a 0.8-line or greater difference in mean visual acuity between the test lens and control lens groups, assuming a standard deviation of 1.6 lines.

[REDACTED]

APPENDIX A SUMMARY OF PROCEDURES REQUIRED AT EACH VISIT

| [REDACTED] | [REDACTED] | [REDACTED] | [REDACTED] | [REDACTED] |
|------------|------------|------------|------------|------------|
| [REDACTED] | [REDACTED] | [REDACTED] | [REDACTED] | [REDACTED] |
| [REDACTED] | [REDACTED] | [REDACTED] | [REDACTED] | [REDACTED] |
| [REDACTED] | [REDACTED] | [REDACTED] | [REDACTED] | [REDACTED] |
| [REDACTED] | [REDACTED] | [REDACTED] | [REDACTED] | [REDACTED] |
| [REDACTED] | [REDACTED] | [REDACTED] | [REDACTED] | [REDACTED] |
| [REDACTED] | [REDACTED] | [REDACTED] | [REDACTED] | [REDACTED] |
| [REDACTED] | [REDACTED] | [REDACTED] | [REDACTED] | [REDACTED] |
| [REDACTED] | [REDACTED] | [REDACTED] | [REDACTED] | [REDACTED] |
| [REDACTED] | [REDACTED] | [REDACTED] | [REDACTED] | [REDACTED] |
| [REDACTED] | [REDACTED] | [REDACTED] | [REDACTED] | [REDACTED] |
| [REDACTED] | [REDACTED] | [REDACTED] | [REDACTED] | [REDACTED] |
| [REDACTED] | [REDACTED] | [REDACTED] | [REDACTED] | [REDACTED] |
| [REDACTED] | [REDACTED] | [REDACTED] | [REDACTED] | [REDACTED] |
| [REDACTED] | [REDACTED] | [REDACTED] | [REDACTED] | [REDACTED] |
| [REDACTED] | [REDACTED] | [REDACTED] | [REDACTED] | [REDACTED] |
| [REDACTED] | [REDACTED] | [REDACTED] | [REDACTED] | [REDACTED] |
| [REDACTED] | [REDACTED] | [REDACTED] | [REDACTED] | [REDACTED] |
| [REDACTED] | [REDACTED] | [REDACTED] | [REDACTED] | [REDACTED] |
| [REDACTED] | [REDACTED] | [REDACTED] | [REDACTED] | [REDACTED] |
| [REDACTED] | [REDACTED] | [REDACTED] | [REDACTED] | [REDACTED] |

[REDACTED]

[REDACTED]

[REDACTED]

APPENDIX B EQUIPMENT LIST

The following equipment will be supplied to an investigative site for the duration of the study provided that the site does not already have such equipment available for use. This equipment loan will be documented in the Clinical Trial Agreement, which indicates that the equipment is to be returned to JJSV at the completion of the study.

- [REDACTED]
- [REDACTED]
- [REDACTED]
- [REDACTED]
- [REDACTED]
- [REDACTED]
- [REDACTED]
- [REDACTED]
- [REDACTED]
- [REDACTED]

[REDACTED]

■ [REDACTED]

■ [REDACTED]

■ [REDACTED]

■ [REDACTED]

■ [REDACTED]

c. [REDACTED]

■ [REDACTED]

■ [REDACTED]

- 5) [REDACTED]
[REDACTED]
[REDACTED]

[REDACTED]

[REDACTED]

| | | |
|------------|------------|------------|
| [REDACTED] | [REDACTED] | [REDACTED] |
| [REDACTED] | [REDACTED] | [REDACTED] |
| [REDACTED] | [REDACTED] | [REDACTED] |
| [REDACTED] | [REDACTED] | [REDACTED] |
| [REDACTED] | [REDACTED] | [REDACTED] |
| [REDACTED] | [REDACTED] | [REDACTED] |
| [REDACTED] | [REDACTED] | [REDACTED] |
| [REDACTED] | [REDACTED] | [REDACTED] |
| [REDACTED] | [REDACTED] | [REDACTED] |
| [REDACTED] | [REDACTED] | [REDACTED] |
| [REDACTED] | [REDACTED] | [REDACTED] |
| [REDACTED] | [REDACTED] | [REDACTED] |
| [REDACTED] | [REDACTED] | [REDACTED] |
| [REDACTED] | [REDACTED] | [REDACTED] |

[REDACTED]

[REDACTED]

| | |
|-------------|------|
| V K O Z S | 32 |
| ● R Z N D O | 25 |
| H O Z S D | 20 |
| S V N Z C | 16 |
| C D V S O | 12.5 |
| O N Z D K | 10 |

[REDACTED]

[REDACTED]

[REDACTED]

[REDACTED]

APPENDIX F INSTRUCTIONS FOR DISTANCE VISUAL ACUITY TESTING

[REDACTED]

[REDACTED]

[REDACTED]

Distance visual acuity measurements are to be performed per the visit schedule in **Appendix A**. To test subjects monocularly, occlude the second eye in the phoropter or with an occluder if trial lenses are used.

[REDACTED]

APPENDIX G INSTRUCTIONS FOR VISUAL ACUITY TESTING [REDACTED]

[REDACTED]
[REDACTED]
[REDACTED]
[REDACTED]
[REDACTED]

[REDACTED]
[REDACTED]
[REDACTED]
[REDACTED]

Visual acuity measurements are to be performed per the visit schedule in **Appendix A**.

[REDACTED]
[REDACTED]
[REDACTED]
[REDACTED]
[REDACTED]
[REDACTED]

[REDACTED]
[REDACTED]
[REDACTED]
[REDACTED]

APPENDIX H INSTRUCTIONS FOR VISUAL ACUITY TESTING [REDACTED]

[REDACTED]
[REDACTED]
[REDACTED]
[REDACTED]
[REDACTED]

[REDACTED]
[REDACTED]
[REDACTED]
[REDACTED]

Visual acuity measurements [REDACTED] are to be performed per the visit schedule in **Appendix A.**

[REDACTED]
[REDACTED]
[REDACTED]
[REDACTED]
[REDACTED]
[REDACTED]

APPENDIX I INSTRUCTIONS FOR VISUAL ACUITY TESTING AT 40 CM

[REDACTED]

[REDACTED]

Visual acuity measurements at 40 cm are to be performed per the visit schedule in **Appendix A.**

[REDACTED]

[REDACTED]

[REDACTED]

[REDACTED]

[REDACTED]

[REDACTED]

[REDACTED]

[REDACTED]

[REDACTED]

[figure not shown]
[REDACTED]

[REDACTED]

[REDACTED]

APPENDIX L SLIT-LAMP EXAM RATINGS

A. Ratings of Aqueous Cells and Flare

CELLS

| Grade | Cells in Field (Field is a 1x1 mm slit beam) |
|-------|--|
| 0 | <1 |
| 0.5+ | 1 - 5 |
| 1+ | 6 - 15 |
| 2+ | 16 - 25 |
| 3+ | 26 - 50 |
| 4+ | >50 |

FLARE

| Grade | Description |
|-------|--|
| 0 | None |
| 1+ | Faint |
| 2+ | Moderate (iris and lens details clear) |
| 3+ | Marked (iris and lens details hazy) |
| 4+ | Intense (fibrin or plastic aqueous) |

B. Ratings of Corneal Edema

Corneal edema should be classified according to the haziness of the epithelium, the number of microcysts observed, and the clouding of the stroma.

| Amount | Grade | Description |
|--------|-------|--|
| None | 0 | Normal transparency: a. No epithelial or sub-epithelial haziness b. No microcysts c. No stromal cloudiness |
| Trace | +1 | a. Barely discernible localized epithelial or sub-epithelial haziness, and/or b. 1 to 20 microcysts, and/or c. Barely discernible localized stromal cloudiness |
| Mild | +2 | a. Faint but definite localized or generalized epithelial, sub-epithelial or stromal haziness/cloudiness, and/or b. 21-50 microcysts |

| | | |
|-----------------|-----------|--|
| Moderate | +3 | a. Significant localized or generalized epithelial, sub-epithelial or stromal haziness/cloudiness and/or b. 51-100 microcysts |
| Severe | +4 | a. Definite widespread epithelial or stromal cloudiness, giving dull glass appearance to cornea or numerous coalescent bullae (please note the number and location of bullae), and/or b. >100 microcysts or bullae, and/or c. Numerous striae (please note the number and location of striae or folds) |

C. Posterior Capsule Striae Grading Scale

The following five-point grading scale is to be used for rating striae in the posterior capsule:

| Amount | Grade | Description |
|----------|-------|--|
| None | 0 | None |
| Trace | +1 | One detectable, barely noticeable striae |
| Mild | +2 | One or two prominent striae |
| Moderate | +3 | Three or more prominent striae, but visibility of retina is not impacted |
| Severe | +4 | Three or more prominent striae affecting visualization of retina |

D. Posterior Capsule Opacification Grading Scale

Below is the five-point grading scale to be used for PCO determination:

| Amount | Grade | Description |
|----------|-------|---|
| None | 0 | Normal posterior capsule with no area of opacity. Red reflex bright. |
| Trace | +1 | Some loss of transparency involving the posterior capsule. Red reflex fairly bright |
| Mild | +2 | Mild loss of transparency with cloudiness extending through most of the posterior capsule. There may be a few Elschnig's pearls in the posterior capsule. Red reflex mildly diminished. |
| Moderate | +3 | Moderate loss of transparency with difficulty visualizing the retina. There may be multiple Elschnig's pearls in the posterior capsule. Red reflex markedly diminished. |
| Severe | +4 | Posterior capsule very opaque with inability to view the retina. The posterior capsule may have confluent |

| | | |
|--|--|--|
| | | Elschnig's pearls and fibrous scarring. Red reflex barely visible. |
|--|--|--|

E. IOL Glistenings

Use the following scale to grade IOL glistenings, using a slit beam 2.0 mm wide and 10.0 mm long:

| Amount | Grade | Description |
|----------|-------|---------------------------|
| None | 0 | No glistenings visible |
| Rare | +0.5 | <10 glistenings visible |
| Trace | +1 | 10-19 glistenings visible |
| Mild | +2 | 20-29 glistenings visible |
| Moderate | +3 | 30-39 glistenings visible |
| Severe | +4 | ≥40 glistenings visible |

APPENDIX M [REDACTED]
[REDACTED]

[REDACTED]
[REDACTED]
[REDACTED]

[REDACTED]
[REDACTED]
[REDACTED] [REDACTED]
[REDACTED]

[REDACTED]

[REDACTED]

[REDACTED]

[REDACTED]

[REDACTED]

[REDACTED]

[REDACTED]

[REDACTED]

[REDACTED]

[REDACTED]

[REDACTED]

[REDACTED]

[REDACTED]

[REDACTED]

[REDACTED]

[REDACTED]

[REDACTED]

[REDACTED]

[REDACTED]

[REDACTED]

[REDACTED]

[REDACTED]

[REDACTED]

[REDACTED]

[REDACTED]

[REDACTED]

[REDACTED]

[REDACTED]

[REDACTED]

- [REDACTED]
- [REDACTED]
- [REDACTED]
- [REDACTED]
- [REDACTED]

[REDACTED]

[REDACTED]

[REDACTED]

[REDACTED]

[REDACTED]

[REDACTED]

[REDACTED]

[REDACTED]

[REDACTED]

[REDACTED]

[REDACTED]

[REDACTED]

[REDACTED]

[REDACTED]

[REDACTED]

[REDACTED]

[REDACTED]

[REDACTED]

[REDACTED]

[REDACTED]

[REDACTED]

[REDACTED]

[REDACTED]

[REDACTED]

[REDACTED]

[REDACTED]

[Redacted text block]

[Redacted text block]

[Redacted text block]

[Redacted text block]

[Redacted text block]

[Redacted text block]

[Redacted text block]

[Redacted text block]

[Redacted text block]

[Redacted text block]

[Redacted text block]

[Redacted text block]

[Redacted text block]

[Redacted text block]

[REDACTED]

[REDACTED]

[REDACTED]

[REDACTED]

[REDACTED]

[REDACTED]

[REDACTED]

[REDACTED]

[REDACTED]

[REDACTED]

[REDACTED]

[REDACTED]

[REDACTED]

[REDACTED]

[REDACTED]

[figure not shown]

1. [REDACTED]
[REDACTED]

[figure not shown]
- [REDACTED] [REDACTED]
- [REDACTED] [REDACTED]
- [REDACTED] [REDACTED]

■ [REDACTED]
[REDACTED]

- [REDACTED] [REDACTED] [REDACTED] [REDACTED] [REDACTED]
- [REDACTED] [REDACTED] [REDACTED] [REDACTED] [REDACTED]
- [REDACTED] [REDACTED] [REDACTED] [REDACTED] [REDACTED]
- [REDACTED] [REDACTED] [REDACTED] [REDACTED] [REDACTED]

■ [REDACTED]
[REDACTED]

- [REDACTED] [REDACTED] [REDACTED] [REDACTED] [REDACTED]
- [REDACTED] [REDACTED] [REDACTED] [REDACTED] [REDACTED]
- [REDACTED] [REDACTED] [REDACTED] [REDACTED] [REDACTED]
- [REDACTED] [REDACTED] [REDACTED] [REDACTED] [REDACTED]

■ [REDACTED]
[REDACTED]
[REDACTED]

1 INTRODUCTION

This document summarizes the statistical methods for analyses of effectiveness and safety data for the TECNIS Eyhance Intraocular Lenses in clinical study (protocol EMON-101-EHCE). This study is a 6-month, prospective, multicenter, bilateral, randomized, subject- and evaluator-masked clinical trial conducted at up to 15 sites in the USA. Subjects will be randomly assigned to receive the study Eyhance IOL or the control monofocal IOL. Up to 220 (110 test, 110 control) subjects will be enrolled in order to achieve 200 treated subjects at 6 months. No site may enroll more than 25% of the total sample size.

1.1 STUDY OBJECTIVES

The purpose of this clinical study is to compare the clinical outcomes for subjects bilaterally implanted with the TECNIS Eyhance Intraocular Lenses to those bilaterally implanted with TECNIS 1-piece Intraocular Lenses. All study endpoints will be evaluated at 6-months postoperative.

1.2 STUDY ENDPOINTS

PRIMARY EFFECTIVENESS ENDPOINT

The primary safety endpoint is the mean monocular first-eye best-corrected distance visual acuity (BCDVA) at 6 months.

SECONDARY EFFECTIVENESS ENDPOINTS

The secondary effectiveness endpoints are:

1.	The mean monocular first-eye distance corrected intermediate visual acuity
	(DCIVA) at 66 cm at 6 months.

SAFETY ENDPOINTS

- Rate of secondary surgical interventions related to optical properties of the lens
- Rate of SPE-type adverse events (first-eye) vs. ISO SPE rates
- Rate of monocular (first-eye) BCDVA

OTHER ENDPOINTS

[figure not shown]
•	
-	
_	
_	

•	

1.3 RANDOMIZATION AND MASKING

A randomization list stratified by investigational sites was created by a JJSV biostatistician who is independent and not involved in the study activities. Subjects will be randomized to TECNIS Eyhance IOL or the control IOL in 1:1 ratio. Unmasked study personnel at the site will be trained to the randomization process through the EDC system and will randomize subjects after the subject has signed the informed consent form, has met all eligibility criteria and the investigator has documented which eye will be the first implanted.

Recommended steps to maintain masking include ensuring that all items pertaining to lens group assignment and lens implantation records are kept separately from all other study documents and subject medical records until after completion of the final study visit.

2.3 VISIT WINDOWS

Appendix I lists the planned analysis tables including the endpoints, the populations and missing data handling rules used.

All subjects will undergo a minimum of 5 visits: Preoperative for both eyes, 1st eye operative, 2nd eye operative, postoperative for at 1 month and 6 months. The exact number of days allowed for each interval is described in the protoco. The number of eyes with missing visits or data outside of the visit interval will be reported.	ol.
2.4 DATA CONVENTIONS For visual acuity data, Snellen acuity will be converted to LogMAR prior to analysis ⁴ . Formulas used for visual acuity analysis are included in Appendix II. For refractive dat all values will be converted to plus cylinder Formulas used for refractive data are also included in Appendix II.	
4	

3 ACCOUNTABILITY/ENROLLMENT

Descriptive statistics will typically include sample size (N), mean, standard deviation (SD), median, minimum (Min.), and maximum (Max.) as appropriate for continuous variables. For categorical data, the counts and percentages will be computed.

3.1 ACCOUNTABILITY

All summaries will be by OVD group. The number of enrolled subjects will be tabulated by site. Subject accountability will be summarized as a frequency distribution (counts and percentages) by scheduled visits. A frequency table will be generated, showing the number of available eyes (those in interval and outside of the interval) and the number of missing and active subjects.

4 DEMOGRAPHICS AND PREOPERATIVE/OPERATIVE PARAMETERS

Subject demographic data including age, sex, race, iris color and ethnicity will be
presented by IOL group. Age will be categorized by less than 60, 60-69, 70-79 and ≥ 80
years old. In addition, age will be summarized with descriptive statistics. The frequency
distribution of sex, race, iris color and ethnicity will also be tabulated. To ensure
comparable demographic characteristics between groups, statistical testing will be
performed.

Deviations from the proposed statistical guidelines will be substantiated by sound statistical rationale. In this study, unless otherwise indicated, two-sample t-tests will be used for continuous data, Wilcoxon rank sum test for ordinal data and Fisher's Exact test for categorical data.

5 POSTOPERATIVE ANALYSES – PRIMARY/SECONDARY ENDPOINTS

5.1 PRIMARY EFFECTIVENESS ENDPOINT

The primary effectiveness endpoint is the mean monocular first-eye best-corrected distance visual acuity at 4 m under photopic conditions at 6 months. The non-inferiority comparison between the IOL groups will be conducted using the two-sided 90% confidence interval on the mean BCDVA difference based on a t-distribution. The mean, SD, median, minimum, maximum and two-sided 90% C.I. will be presented by IOL

group. Note that lower logMAR value is a better acuity and a higher logMAR value is a poorer acuity. The null hypothesis is that the mean difference between the test and control IOLs is less than or equal to -0.1 logMAR, with the alternative hypothesis being that the mean difference is greater than -0.1 logMAR. A lower bound of the two-sided 90% confidence interval will be used for evaluation based on a two-sample t-test statistic. The success criterion is that the lower limit of the two-sided 90% confidence interval is above -0.1 logMAR.

```
H_o: \mu_c - \mu_t \le -0.10 (test is inferior (higher logMAR value) to control)

H_1: \mu_c - \mu_t > -0.10 (test is not inferior (lower logMAR value) to control)
```

where

```
\mu_t = the mean logMAR BCDVA for test group \mu_c = the mean logMAR BCDVA for control group
```

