10.4 RANDOMIZATION AND MASKING

A randomization list will be created by the JJSV biostatistician for each investigative site and the randomization code will be uploaded into the electronic data capture system (EDC). [REDACTED]

[REDACTED]

As part of the informed consent process, the investigator or delegate will explain to the subject the requirements of a randomized study and the differences expected between the two lens models in the study: TECNIS Eyhance lens and the control lens. [REDACTED]

[REDACTED]

The subjects and the study technicians performing the postoperative vision tests are to be masked through study completion. [REDACTED]

[REDACTED]

[REDACTED] Following completion of the final study exam, each subject will be given the permanent IOL implant identification card.

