15.2 ADMINISTRATIVE MONITORING

Administrative monitoring procedures will ensure that study devices, subjects, and forms can be traced and will allow monitoring of investigator progress and compliance.

Device Accountability

Lens accountability will be maintained at the investigative site by keeping records for all study lenses implanted. Study lens information will be maintained in the subject accountability study binder and will be reviewed during periodic investigative site monitoring visits.

[REDACTED]

[REDACTED]

The Sponsor will also review source documents to verify that all required items have been documented in the subject medical charts. Refer to Section 14.1, Source Documents, for a list of items that are required for source documentation. In addition to subject files, study logs will be checked and conformance to lighting levels for visual acuity tests will be verified.

[REDACTED]

Upon study completion, a site visit will be made to each site to monitor the last of the subject data records and finalize any outstanding study issues.

A separate Study Monitoring Plan will be established prior to study start that will define the type and frequency of monitoring visits and frequency of record monitoring.

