5.2 SECONDARY EFFECTIVENESS ENDPOINTS

MEAN DISTANCE-CORRECTED INTERMEDIATE VISUAL ACUITY AT 66 CM (DCVA66)

The first secondary effectiveness endpoint is the mean monocular first-eye distance-corrected intermediate visual acuity at 66 cm under photopic conditions at 6 months. The DCVA66 will be summarized (n, mean, SD, median, minimum, maximum) with the two-sided 95% CI by IOL group. Comparisons of mean DCVA66 between the test and control groups at 6 months will be performed using a two-sample t-test with a one-sided alpha level of 0.025.

The null hypothesis is that the mean monocular DCVA66 logMAR value for eyes in the test group is worse than or equal to that for the control group. The alternate hypothesis is that the mean monocular DCVA66 logMAR value for the test group is better than that for the control group.

```
H_o: \mu_c - \mu_t \le 0 (test is worse than (higher LogMAR value) or equal to control) H_1: \mu_c - \mu_t > 0 (test is better (lower LogMAR value) than control)
```

where

```
\mu_t = the mean LogMAR DCVA66 for test group \mu_c = the mean LogMAR DCVA66 for control group
```

The success criterion is a statistically significantly better mean DCVA66 (lower LogMAR value) for test lens compared to the control lens group ($p \le 0.025$).

case population will also be used in the analysis of BCDVA vs. ISO SPE rate. First-eye data will be the primary analysis for safety endpoints.

SECONDARY SURGICAL INTERVENTION RELATED OPTICAL PROPERTIES OF THE LENS

The counts and percentages of secondary surgical interventions (SSIs) related to optical properties of the lens will be reported by IOL group.

SPE RELATED ADVERSE EVENT VS. ISO SPE RATES

The counts and percentages of SPE-type adverse events will be reported by IOL group. The rate in the test lens group will be compared to the ISO Safety and Performance Endpoints (SPE) rates listed in ISO 11979-7 using two-sided 90% Clopper Pearson Exact confidence interval with no CIs multiplicity adjustment.

Success criteria is that the SPE grid that the lower two-sided 90% confidence limit of the test group is lower than the SPE rate.

MONOCULAR BCDVA VS. ISO SPE RATES

The counts and percentages of monocular BCDVA will be presented by IOL group. The rate in the test lens group will be compared to the ISO SPE grid using two-sided 90% Clopper Pearson Exact confidence interval with no CIs multiplicity adjustment.

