8.2 MONOCULAR DISTANCE-CORRECTED INTERMEDIATE VISUAL ACUITY AT 66 CM (DCVA66)

For monocular distance-corrected intermediate visual acuity at 66 cm, with 100 subjects in each lens group, there is over 90% power at one-sided 0.025 alpha to detect a 0.8-line or greater difference in mean visual acuity between the test lens and control lens groups, assuming a standard deviation of 1.6 lines.

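### Randomisation is stratified by site, but the visible decision tests for BCDVA and DCVA66 leave site out; if sites differ, the intervals are somewhat wider than they need to be

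*SAP*

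**What the plan says.** - **Randomisation.** SAP 1.3: "A randomization list stratified by investigational sites was created by a JJSV biostatistician who is independent and not involved in the study activities"; allocation is 1:1. Protocol 10.4 agrees: "A randomization list will be created by the JJSV biostatistician for each investigative site".
- **Primary decision.** SAP 5.1, and protocol 20.3 in the same terms, judges BCDVA non-inferiority on a 90% interval: "A lower bound of the two-sided 90% confidence interval will be used for evaluation based on a two-sample t-test statistic". The lower limit for control minus test must lie above -0.1 logMAR.
- **Secondary decision.** In SAP 5.2 and protocol 20.3, the DCVA66 comparison "will be performed using a two-sample t-test with a one-sided alpha level of 0.025".
- **Site.** None of these rules names site. Protocol 20.4 says, for the primary and secondary endpoints: "A mixed effect model will be used to evaluate site heterogeneity by investigation of site effect and site by group interaction effect". That sentence presents the model as a heterogeneity check; the text after it is blacked out.
- **Size and spread.** Up to 15 sites, at least 100 evaluable subjects per group, and "No site may enroll more than 25% of the total sample size" (SAP 1).

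**The concern.** Stratified allocation balances the lens groups within each site, so differences in mean acuity between sites largely cancel out of the group difference. A two-sample t-test does not know this: its pooled SD still includes the between-site variation. The reported standard error is then larger than the true error, the interval is too wide, and the actual error rate falls below nominal. The design pays for stratification and the decisive analysis does not use it.

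At stake is some precision, mainly for DCVA66. There is also an open question in the visible text: which result governs if the t-test and the site model of protocol 20.4 disagree.

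**Working it through.** **Inputs.** From SAP 8.1 and 8.2 (also protocol 20.7): 100 subjects per group. BCDVA: SD 1.2 lines, margin 1 line, true difference 0, one-sided 0.05. DCVA66: SD 1.6 lines, difference 0.8 lines, one-sided 0.025. One line is 0.1 logMAR. Up to 15 sites, largest at most 25% (SAP 1). Assumed, because the visible text does not give them: the share ρ of total variance lying between sites, the block size, and the distribution of subjects over sites. The planning SDs are read as total SDs.

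**Step 1: the plan's own power.** SE = SD × √(2/100), with noncentral t on 198 df.
- BCDVA: SE = 1.2 × 0.1414 = 0.1697 lines; 1/0.1697 = 5.89; power 99.999%.
- DCVA66: SE = 1.6 × 0.1414 = 0.2263 lines; 0.8/0.2263 = 3.54; power 94.0%.

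SAP 8.2 states for DCVA66 that "there is over 90% power at one-sided 0.025 alpha to detect a 0.8-line or greater difference in mean visual acuity", and SAP 8.1 makes the same power claim for BCDVA. Both reproduce.

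**Step 2: closed form, perfect balance within site.** Half-width without site is t(198) × SE. With 15 fixed site effects it is t(184) × SE × √(1-ρ), since 198 - 14 = 184. For DCVA66 at ρ = 0.10: 1.972 × 0.2263 = 0.446 lines against 1.973 × 0.2263 × 0.9487 = 0.424, a ratio of 1.054. The t-test's actual one-sided error is about 1 - Φ(1.972/0.9487) = 1.9%. At ρ = 0.05 and 0.20 the same formulas give 2.5% and 11.8% wider, with errors of 2.2% and 1.4%.

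**Step 3: simulation.** 40,000 replicates in each of 30 settings: five values of ρ; blocks of 2, 4 and 6; and 15 sites of 13 to 14 subjects, or of 50 down to 2 (the largest at the 25% cap). The comparison is the pooled t-test against lens group plus fixed site, with no pooling of sites. Ranges cover all block and site-size settings.

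| ρ | t-test interval vs adjusted | t-test error, nominal 2.5% | t-test error, nominal 5% | DCVA66 power, t-test vs adjusted |
|---|---|---|---|---|
| 0 | adjusted is 0.2% to 0.7% wider | nominal | nominal | 0.1 to 0.4 points higher |
| 0.01 | no real difference | – | – | – |
| 0.05 | 1.5% to 2.2% wider | 2.2% to 2.3% | 4.5% to 4.7% | 0.1 to 0.5 points lower |
| 0.10 | 4.0% to 4.9% wider | 2.0% to 2.1% | 4.2% to 4.4% | 0.8 to 0.9 points lower |
| 0.20 | 9.6% to 10.9% wider | 1.6% to 1.7% | 3.4% to 3.7% | 1.4 to 1.7 points lower |

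Adjusted error was 2.4% to 2.7% and 4.7% to 5.3% across all settings. The Monte Carlo standard error is 0.08 points at 2.5%, and 0.11 at 5% and at 95% power.

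**Step 4: in lines, equal sites, blocks of 4.** At ρ = 0.10 the DCVA66 standard error is 0.2253 against 0.2149 (ratio 1.048), the 95% half-width 0.444 against 0.424, and power 94.9% against 95.8%. At ρ = 0.20 power is 95.7% against 97.4%. For BCDVA at ρ = 0.10 the 90% half-width is 0.279 against 0.266, with a margin of 1 line; the lowest simulated BCDVA power in any setting was 99.997%.

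The closed form runs slightly above the simulation because it is an ideal case. It uses the full total SD (0.2263 against a simulated 0.2253) and exact balance within sites (0.2263 × 0.9487 = 0.2147 against 0.2149).

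**The case against.** A prespecified two-sample t-test is valid, errs on the safe side and matches the method behind the sample size. The strongest points against changing it are these:

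- **No decision consequence for the primary endpoint.** This stands: a change of 0.013 lines in half-width (0.279 - 0.266) is immaterial against a 1-line margin.
- **The gain rests on an unknown.** This stands. No document gives a between-site variance, and the plan standardises testing: a fixed photopic luminance range and a common testing system (protocol 10.7), and at monitoring "conformance to lighting levels for visual acuity tests will be verified" (protocol 15.2). The true share may be small, and at zero the adjusted analysis is marginally worse. The ranges above are not bounds.
- **Nothing is lost against the plan.** This stands: unadjusted DCVA66 power is 93.9% to 96.0% throughout.
- **The plan may already deal with it.** This cannot be settled. The visible sentence of protocol 20.4 does not make the site model decisive, but the blacked-out text might.
- **The model in 20.4 is not the one proposed.** This is correct: it is a mixed model with an interaction, whereas the proposal is additive with fixed sites.

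These points limit the importance of the finding. They do not remove the mismatch between the stratified design and the visible tests.

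**Conclusion.** The point holds for the visible text, as an efficiency and alignment matter and not a validity error. If sites account for 5% to 20% of total variance, leaving site out widens the intervals by roughly 2% to 11% and costs at most 1.7 points of DCVA66 power; at 1% or less there is nothing to gain. The BCDVA conclusion is practically unaffected. The figures assume 200 evaluable subjects, 15 sites, permuted blocks of 2 to 6 and the planning SDs as total SDs. The change is worth making because the trade is lopsided: under 1% of width if sites do not differ, against a real gain at correct nominal error if they do.

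**What to change.** In protocol 20.3 and SAP 5.1 and 5.2, specify that the group difference, confidence interval and p-value come from a linear model with lens group and site, keeping the present margin and alpha levels. Add a rule for small sites, fixed before unmasking; for example, combine sites with fewer than 2 evaluable subjects in either group, the threshold being the sponsor's choice. Keep the two-sample t-test as a sensitivity analysis, and state how the heterogeneity model of protocol 20.4 relates to the decisive one. If the blacked-out part of 20.4 already makes a site-adjusted estimate decisive, bring 20.3, 5.1 and 5.2 into line with it.

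Cost: one model statement, the pooling rule, and whatever approval the sponsor needs to change the protocol text. The model uses up to 14 of 198 degrees of freedom. If sites do not differ, the interval is 0.2% to 0.7% wider, the upper end applying to very unequal sites without pooling. No extra data or subjects are needed.
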